**2.3.2. Risk Assessment****Table 1: Risks and Mitigation Strategies**

Potential Risk	Rationale / Summary of Data	Mitigation Strategy
1. Severe hypersensitivity including anaphylaxis	Administration of therapeutic proteins, including monoclonal antibodies such as CSL312, is associated with the risk of hypersensitivity and anaphylactic reactions, some of which can be serious and life-threatening.	The first dose of CSL312 will be performed at the site under medical supervision with immediate access to emergency equipment and medication for the treatment of severe hypersensitivity including anaphylaxis. Subjects will be informed of the early signs of hypersensitivity reactions including hives, generalized urticaria, tightness of the chest, wheezing, hypotension, and anaphylaxis. Subjects will be required to remain at the site for monitoring for approximately 2 hours following the first dose administration.  To date, no related severe hypersensitivity or anaphylactic type reactions have been observed after repeated administration of CSL312 in the completed or ongoing clinical trials.
2. Immunogenicity (antidrug antibodies)	All protein therapeutics are potentially immunogenic. Because CSL312 is a protein, it has the potential to cause the development of neutralizing and non-neutralizing ADAs.	The development of ADAs throughout the study will be monitored.  To date, based on all available data, there is a low risk for the development of immunogenicity with CSL312.

ADA = antidrug antibody.

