### 5.1. Inclusion Criteria

To be enrolled into the study, subjects must meet all the following inclusion criteria:

1. The subject's parent(s) or legally authorized representative(s) is capable of providing written informed consent for study participation before undergoing any study-specific assessments or procedures; subjects will provide assent for study participation according to local regulations.
2. Male or female.
3. Aged 2 to 11 years, inclusive, with body weight  $\geq 10^{\text{th}}$  percentile based on age (according to the Centers for Disease Control growth charts [[CDC, 2017](#)]), at the time of providing written informed consent / assent.
4. Diagnosed with clinically confirmed C1-INH HAE:
  - a. Documented clinical history consistent with HAE (SC or mucosal, nonpruritic swelling episodes without accompanying urticaria), and
  - b. C1-INH antigen and / or functional activity  $\leq 50\%$  of normal as documented in the subject's medical records, and
  - c. C4 antigen concentration below the lower limit of the reference range as documented in the subject's medical records.
5. Experienced  $\geq 2$  HAE attacks during the 6 months before Screening, as documented in the subject's medical records.

**NOTE 1:** For subjects taking any prophylactic HAE therapy during the 6 months before Screening,  $\geq 2$  HAE attacks may be documented over 6 months before commencing the prophylactic therapy.

**NOTE 2:** If clinical confirmation of C1-INH HAE in the medical records is from 5 years or more ago (for subjects 6 to 11 years of age) or not available (for subjects 2 to 5 years of age), a blood sample to confirm the HAE disease will be collected at Screening.

6. Investigator believes that the subject (or the subject's legally authorized representative[s]) understands the nature, scope, and possible consequences of the study.

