**Table 8: Hereditary Angioedema Symptom / Location Associated with a Hereditary Angioedema Attack**

	Peripheral Attack Symptoms (Cutaneous)	Abdominal Attack Symptoms	Laryngeal Attack Symptoms
Locations	
 
• Head
 
• Face (external): lips, nose, cheeks, or eyes
 
• Neck
 
• Arms / hands
 
• Chest, shoulder, or back
 
• External abdominal area
 
• External genitourinary areas (buttocks)
 
• Legs / feet
 
• Others
 
	
 
• Internal abdomen (including, but not limited to, the intestine, the bladder, and / or testicles or uterus)
 
• Internal genitourinary (including, but not limited to, the penis and / or scrotum, or the labia and / or vulva)
 
	Face internal or upper airway / throat: 
 
• Tongue / palate / inside mouth
 
• Nasal cavity
 
• Throat / voice box
 
• Uvula
 
• Larynx
 

Symptoms	
 
• Pain / discomfort
 
• Skin swelling
 
• Itching / irritation
 
• Tight skin
 
• Burning
 
• Redness / rash
 
	
 
• Pain / cramping / discomfort
 
• Vomiting / nausea
 
• Abdominal swelling / bloating / tightness / hard stomach
 
• Diarrhea
 
• Gassy
 
• Low blood pressure
 
• Pass out / feel dizzy
 
	
 
• Difficulty breathing (dyspnea), speaking, or swallowing
 
• Voice change
 
• Stridor / wheezing
 
• Throat tightening
 
• Turning blue
 

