## 2.4 Attack Assessment / Confirmation by the Investigator

The investigator or delegate at each site will review the HAE symptoms reported by the subject in the eDiary and confirm an HAE attack(s) if applicable. It is recommended that the sites limit the number of experienced individuals responsible for assessing subject-reported symptoms to 1 or 2 individuals, where 1 of them should be the investigator. The assessors must be experienced with HAE and familiar with the study subject's disease history.

Each time the investigator / delegate contacts the subject or at a site visit, he / she will review the subject's eDiary entries. Additionally, the subject will be reminded to have his / her eDiary entries up-to-date and to check that symptoms indicative of an HAE attack are documented as instructed. The investigator / delegate may ask additional probing questions about the HAE symptoms experienced by the subject to assist his / her assessment of the symptoms and rule out if there are any possible alternative etiologies of the symptoms, eg, whether only prodromal symptoms were experienced and / or if anything is different from previous experiences.

Each individual HAE attack must be associated with at least 1 symptom or location but may be associated with multiple symptoms. These symptoms may develop concurrently or consecutively within 24 hours. If the investigator confirms an HAE attack, this should be reported in the Case Report Form (CRF) as a single HAE attack, including the symptom(s) associated with the attack. If there has been a completely symptom-free 24-hour minimum separation between the resolution of the prior attack and the onset of next attack, this new set of symptoms would constitute a new event and should be reported as a separate single attack if the investigator confirms the HAE attack.

The investigator will determine if the symptoms reported by the subject did not represent an HAE attack, eg, if the symptoms are not typical of an attack or if there is a more likely alternative cause for the symptoms, or if the symptoms did not resolve following the administration of the on-demand medication. Examples are throat irritation due to an upper respiratory illness or abdominal discomfort due to gastrointestinal upset.

In an effort to maintain consistency across data collection and analysis within this HAE prophylaxis development program, the following recommendations should be followed:

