### **Symptoms Reported as Adverse Events**

The investigator or designee will evaluate the symptom data entered in the eDiary by the subject using the standardized set of requirements to determine if the symptoms reported constitute an HAE attack or not. If the investigator confirms the symptoms as an HAE attack, then the HAE attack will be reported in the CRF. If the assessment of the symptoms is not confirmed as an HAE attack, then the etiology of the symptoms must be reported and recorded as an adverse event.

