Table 5 TEAE Assignment in Case of Missing AE Start Date Elements

Missing elements of AE start	Rule	
Regardless of any missing information for AE start: AE end date / time < IP start date / time		non-TEAE
Otherwise (i.e., if AE end date / time \geq IP start date / time)		
- All		TEAE
- Day and Month	AE start year \geq IP start year	TEAE
	AE start year < IP start year	non-TEAE
- Day	AE start month / year \geq IP start month / year	TEAE
	AE start month / year < IP start month / year	non-TEAE
- Time	AE start date \geq IP start date	TEAE
	AE start date < IP start date	non-TEAE

If AE start dates or end dates are missing or partially missing for an AE, no duration will be calculated. If for a TEAE the relationship to study treatment is missing the worst case will be assumed for summarizing analysis (i.e., the relationship to study treatment will be assumed to be "Related"). In case of missing study treatment relationship for non-treatment-emergent AEs, the relationship will be set to "Not related".

Temporally associated TEAEs are defined as AEs with an onset between the start of the injection and up to 24 hours after the end of the injection. In the case the time of the onset of the AE is missing, the AE is considered temporally associated, if the onset of the AE is between the day of the start of injection and the day of the end of injection + 1 day (inclusive). If the start date of the AE is (partially) missing the temporally association cannot be assessed.

Severe hypersensitivity including anaphylaxis is defined as AESI per study protocol . In addition to AESIs reported by Investigators per study protocol, events suggestive of any hypersensitivity including anaphylaxis will be identified for further review by:

- Standardised MedDRA Query "Hypersensitivity (SMQ)" (broad).
- Anaphylactic reaction (SMQ) (broad).
- Anaphylactic/anaphylactoid shock conditions (SMQ) (broad).

The broad scope includes narrow and broad search. The SMQ search does not account for severity (also non-severe cases will be included) while the AESI assessment by the investigator will do.

TEAE rates per subject year of exposure will be calculated as:

$$\text{TEAE rate per subject year} = \frac{\text{Number of TEAEs}}{\text{Subject Years of Exposure}}$$

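### An ambiguous episode soon after a CSL312 injection, once judged an HAE attack, drops out of every adverse event and hypersensitivity output, and no rule or count uses its timing relative to the dose

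*Protocol*

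**What the plan says.** **The named risk.** Severe hypersensitivity including anaphylaxis is the first risk in Protocol Table 1 (section 2.3.2) and the only AESI (sections 8.4 and 10.2.1.3). Table 1 says subjects will be told the "early signs of hypersensitivity reactions including hives, generalized urticaria, tightness of the chest, wheezing, hypotension, and anaphylaxis".

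**The attack symptoms.** Appendix 2 Table 8 lists "Stridor / wheezing" under laryngeal attacks, "Low blood pressure" under abdominal attacks, and "Itching / irritation" and redness/rash under peripheral attacks. Section 2.4 of the appendix states: "Each individual HAE attack must be associated with at least 1 symptom or location but may be associated with multiple symptoms". By contrast, inclusion criterion 4a (Protocol 5.1) describes the disease history as "nonpruritic swelling episodes without accompanying urticaria".

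**The routing.** Appendix 2, under Symptoms Reported as Adverse Events: "If the investigator confirms the symptoms as an HAE attack, then the HAE attack will be reported in the CRF". The same paragraph sends symptoms to the adverse event record only when they are not confirmed as an attack, and Protocol 8.2 gives the same either/or instruction.

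**The safety outputs.** SAP 10.2: "Temporally associated TEAEs are defined as AEs with an onset between the start of the injection and up to 24 hours" after the injection ends. The SMQ searches are reported as TEAEs (SAP 10.2.2), and AESIs are those the investigator identifies (Protocol 10.2.1.3).

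**The concern.** The signs of the main named risk overlap with the signs of the disease, and the record an episode enters depends on one classification decision. The appendix that governs that decision does not ask when the last injection was given and does not name a drug reaction as a possible explanation. Its examples of other causes are an upper respiratory illness and gastrointestinal upset.

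If a reaction is judged an attack, the error runs in two directions. The safety tables lose an event, which favours the drug. The attack count gains one, which works against it. The first matters more, because TEAEs are a primary endpoint and hypersensitivity is the event the study watches most closely.

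**Working it through.** The plan states no figure on this point and has no sample size calculation to reproduce. The check is a comparison of texts, plus arithmetic for scale.

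**1. Overlap of signs.** Table 1 names five individual signs plus anaphylaxis.
- Wheezing: also in Table 8.
- Hypotension: also in Table 8, as low blood pressure.
- Hives and generalized urticaria: not in Table 8 by name, but partly covered by itching and redness/rash.
- Chest tightness: not in Table 8 as a symptom. Chest appears as a location and throat tightening as a symptom.

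Two of the five match directly and two in part.

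**2. What the classification asks.** The eDiary items, the investigator's follow-up items and the CRF attack fields in Appendix 2 (sections 2.2 and 2.4.1) cover onset, resolution, location, severity, on-demand medication and medical assistance. None asks for the time since the last CSL312 dose.

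**3. Which outputs could find a misfiled episode.** The TEAE tables, the 24-hour temporal rule, the SMQ searches and the temporal criterion for causality (Protocol 10.2.3) all work on adverse events. AESIs are a subset of adverse events. No planned hypersensitivity output reads the HAE Attacks form.

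**4. Doses outside scheduled visits.** For ages 6 to 11, doses run from Day 1 to Month 11, which is 12 doses. Site administration is marked at Day 1 and Months 1, 3, 6 and 9, which is 5. So 12 − 5 = 7 of 12 planned doses fall outside scheduled site visits. For ages 2 to 5, all 6 doses coincide with visits. In both groups a trained caregiver may inject at home after the first dose, at the investigator's discretion.

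**5. Size of one misfiled subject.**
- Subject incidence: 1/20 = 5.0 percentage points (1/15 = 6.7 if the denominator is the 15 planned completers).
- Exact two-sided 95% limits, for scale only: 0/20 has an upper limit of 1 − 0.025^(1/20) = 16.8%; 1/20 has limits of 0.1% and 24.9%. The intervals overlap heavily. What changes is the statement that no case occurred.
- Primary summary, assuming all 20 complete 361 days: 20 × 361/365.25 = 19.77 subject-years, so one missing event lowers the TEAE rate by 1/19.77 = 0.05 per subject-year.

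**6. How many attacks a 24-hour flag would catch by chance.** Assume that attacks are unrelated to dosing and that all doses are given. Treating each window as one day:
- Q1M: 12/361 = 3.3% of attacks.
- Q2M: 6/361 = 1.7%.

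Where the onset time is missing, the SAP's day-based rule covers two calendar days, which doubles these to 24/361 = 6.6% and 12/361 = 3.3%. Either way the review is small.

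**The case against.** The strongest reply is that an experienced assessor makes this decision with several safeguards. Much of that reply stands.

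- **One symptom is not enough.** A reader might infer that a single Table 8 symptom makes an attack. The wording in section 2.4 sets a necessary condition. The investigator must still confirm the attack, Table 8 is described as an aid, and section 2.4.1.3 expects perceivable swelling and/or discomfort in every attack.
- **Other causes are weighed.** Assessors must know HAE and the child's history, and may probe for alternative explanations. Atypical symptoms, or failure to resolve after on-demand medication, count against an attack. The two examples given do not exclude a drug reaction.
- **Dose timing is shown.** A reader might infer that the plan ignores it altogether. The attack listing (SAP 9.2.1) prints the latest dose with its date and time, and a potential trigger. The subject profiles (SAP 9.2.1.5) plot attacks and doses on one axis. The IDMC outputs in SAP 3.5.1 include the attack listing and a subject profile figure.
- **Subject protection does not rest on the form.** A reader might infer that a misfiled reaction cannot reach the individual halting criterion. Protocol 7.1.2.1 turns on what the investigator or sponsor considers related, not on the CRF page used. Adverse events are also sought at every visit, and an eDiary entry alerts the site.
- **Efficacy is affected only in part.** A reader might infer that every efficacy endpoint is inflated. A mild, untreated episode does not enter the moderate/severe or on-demand-treated rates, and the median, which is of primary interest, may not move.
- **One document is not available.** AESIs are identified under a Medical Monitoring Plan that may hold further criteria. Dual reporting is also not expressly forbidden.

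What remains is narrower. None of these safeguards requires a drug reaction to be considered before an attack is confirmed, and no rule, flag or count acts on the timing that is displayed.

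**Conclusion.** The point holds as a gap in classification and analysis. An ambiguous episode soon after a dose that is judged an attack has no planned route into the TEAE, AESI, SMQ or 24-hour outputs.

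Its size depends on one case occurring: 5 percentage points of subject incidence in 20 children, or about 0.05 TEAEs per subject-year if all complete. Only a severe reaction would alter the AESI count; milder ones would be lost from the TEAE and SMQ tables. The documents do not show that misfiling has happened or give a likelihood, and Table 1 reports no related severe hypersensitivity reactions to date. The conclusion also assumes that the Medical Monitoring Plan adds no rule covering confirmed attacks. It is worth correcting because the correction is cheap, not because bias has been shown.

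Separately, itching and redness/rash in Table 8 sit poorly with criterion 4a. One is a reporting aid and the other an eligibility definition, but the two passages need to be reconciled.

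**What to change.** 1. **SAP 10.2.2/10.2.3.** Apply the existing 24-hour rule, including its day-based version for missing times, to investigator-confirmed HAE attacks. Flag, list and count by regimen those with onset from the start of the injection to 24 hours after its end, with the symptom description. Review them before the PARM. Add a sensitivity version of the hypersensitivity table that includes flagged attacks with overlapping symptoms, and fix the list of those symptoms in advance.
2. **Appendix 2, section 2.4.** For an episode in that window, have the assessor document whether a drug reaction was considered and excluded. When it was not excluded, the episode is entered on the adverse event form as well. This concerns recording only.
3. **Table 8 and inclusion criterion 4a.** Reconcile the two on itching and redness/rash.

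The first item needs SAP wording, one listing, one count and one table, from data already collected: attack start time and symptom description (Appendix 2, section 2.4.1) and administration times (SAP 10.1). The other two can go into the next amendment. The downside is that a few true attacks will appear in both the efficacy and the adverse event data. A footnote identifying dual entries would handle this.

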### **Symptoms Reported as Adverse Events**

The investigator or designee will evaluate the symptom data entered in the eDiary by the subject using the standardized set of requirements to determine if the symptoms reported constitute an HAE attack or not. If the investigator confirms the symptoms as an HAE attack, then the HAE attack will be reported in the CRF. If the assessment of the symptoms is not confirmed as an HAE attack, then the etiology of the symptoms must be reported and recorded as an adverse event.

## 2.4.1 Documenting Investigator-confirmed Attacks

Accurate and complete documentation of investigator-confirmed HAE attacks is important for the study as it will be used for the study primary endpoint analysis. All HAE attack information should be substantiated by supporting documentation and medical records.

The site should record the following information on each attack in the CRF:

- Start date and time of an attack
- End date and time of an attack
- Location(s) of HAE symptoms
- HAE symptom description
- HAE attack severity evaluation (refer to [Section 2.4.1.3](#))
- Use of on-demand treatment (if yes, enter the following information in HAE treatment form):
  - Name of on-demand medication
  - Dose(s) of on-demand medication(s) used
  - Route(s) of administration of on-demand medication(s) used
  - Start date and time of administration(s) of on-demand medication(s) used
  - Select the identification number of the HAE attack the on-demand treatment was given for (to be selected from a list) in the CRF
  - Administration of on-demand medication(s) at a study site, home, emergency room

### 2.4.1.1 Attack Duration

The duration of an HAE attack will be reported by the investigator / delegate considering all available medical information, including the onset of first symptom and resolution of last of symptom of each attack entered in the eDiary. Unless there has been a completely symptom-free 24-hour minimum separation between the onset and resolution of all symptoms, a single HAE attack will be documented on the basis of the earliest start and the latest end date of symptoms in the anatomic locations listed.

### 2.4.1.2 Attack Location

HAE attacks can occur in any anatomical location or multiple locations of the body, and these locations are highly variable. An HAE attack may manifest itself in multiple anatomic locations. For example, swelling of the hand and abdomen may occur as symptoms of a single attack if they are temporally associated (ie, occurring at the same time or occurring within overlapping periods within 24 hours). Unless there has been a completely symptom-free 24-hour minimum separation between the onset of new symptom and resolution of prior symptoms in any / all location(s), a single HAE attack will be documented with all relevant locations listed in the CRF.

### **2.4.1.3      Attack Severity**

The severity of each HAE attack (ie, mild, moderate, or severe) will be assessed by the investigator or designee based on the subject's description of the attack. The severity over the time that the attack develops, progresses, and resolves can range from mild to severe. The overall attack severity will reflect the maximum intensity of the attack, as assessed by the investigator.

All attacks regardless of the severity should be associated with perceivable swelling and / or discomfort. Further qualifiers for attack severity are described below. Note that these may vary between subjects and attacks.

- Mild
  - The use of HAE on-demand medication to treat the attack may not be necessary.
  - Other concomitant medication (eg, analgesics) may be used to treat attack symptoms.
- Moderate
  - The HAE attack causes daily activities to be difficult.
  - Some assistance may be needed to complete daily activities.
  - The use of HAE on-demand medication to treat the attack is probable.
- Severe
  - The HAE attack causes marked limitation of daily activities.
  - Medical assistance and intervention may be required, including at clinic emergency room visit or hospitalization.
  - HAE on-demand medication is used to treat the attack.

9.2.1.4	Percentage Reduction in the Time-normalized Number of HAE Attacks	31
9.2.1.5	Supplementary Analysis of Secondary Endpoints	32
9.3	Efficacy – Derived Variables	34
9.4	Multiple Comparisons and Multiplicity.....	36
9.5	Missing Data and Imputation.....	36
9.6	Treatment Compliance.....	36
10	Safety Analyses.....	37
10.1	Extent of Exposure.....	37
10.2	Adverse Events	38
10.2.1	Primary Safety Estimand.....	40
10.2.2	Analysis of Primary Safety Endpoint.....	41
10.2.3	Analysis of Secondary Safety Endpoints	42
10.3	Clinical Laboratory Evaluations	43
10.4	Other Safety Measures	43
10.4.1	Vital Signs	43

10.4.2	Physical Examination.....	43
11	Pharmacokinetic Analyses	44
11.1	Drug Concentration Measures	44
11.2	Deriving and Summarizing Pharmacokinetic Parameters	46
12	Pharmacodynamic and Biomarkers Analyses.....	46
12.1	Pharmacodynamic Analyses	46

List of Tables

Table 1	Primary Study Objectives and Endpoints	11
Table 2	Secondary and Exploratory Study Objectives and Endpoints	12
Table 3	Overview of Study Periods and Time Windows	20
Table 4	Potential Protocol Deviations and/or Reasons for Exclusion From Analysis Sets	25
Table 5	TEAE Assignment in Case of Missing AE Start Date Elements	39

List of Figures

Figure 1	Overall Study Schema.....	10
----------	---------------------------	----

Modification History

Ver-sion	Effective Date	Author of Modification	Summary of Change
1.0	1 August 2023		Not applicable (original version)
2.0	1 July 2024	[name]	
 Changes due to protocol amendments 1 and 2: 
 Sample size. Minor word modifications in the definitions of the Safety Analysis Set and the Per-protocol Analysis Set. CRF version updated. List of IDMC outputs added. EoT Visit date will be set to last IP administration + 30 days or +60 days for Q1M or Q2M, respectively, if the EoT Visit of a subject is delayed by more than the treatment time window relative to the last IP administration. AESI by SMQ search (hypersensitivity) renamed to TEAEs by SMQ search (hypersensitivity).
3.0	5 March 2025	[name]	
 Implementation of protocol amendment 3: 
 Subjects can complete the study without Follow-up after the End of Treatment visit. Description of time windows for efficacy and adverse events added as per TLF shells. Term "Data Review" renamed to "Planned Analysis Review" following Parexel SOP update.

Ver- sion	Effective Date	Author of Modification	Summary of Change
			
• SMQ search renamed to "hypersensitivity including anaphylaxis" for clarification.• Compliance formula for completed subjects in Section 9.6 corrected.• Term "infusion device" modified to "device issues".• Overview table for TEAEs and TEAE table by SOC and PT until Follow-up added.• Minor editorial changes.

1 List of Abbreviations

Abbreviation	Term
ADaM	Analysis Data Model
AE	Adverse event
AESI	Adverse event of special interest
ATC	Anatomical therapeutic chemical
BLQ	Below limit of quantification
BMI	Body mass index
C1-INH	C1-esterase inhibitor
CDISC	Clinical Data Interchange Standards Consortium
CI	Confidence interval
C _{max}	Maximum plasma concentration
COVID-19	Coronavirus disease 2019
CPP	CSL Behring Clinical Pharmacology and Pharmacometrics
CSR	Clinical study report
C _{trough}	Trough plasma concentration
CV	Coefficient of variation
CV%	Percent coefficient of variation
DBL	Database lock
eCRF	Electronic case report form
EoS	End of study
EoT	End of treatment
ESP	External service provider
FXII	Factor XII
FXIIa	Activated factor XII
HAE	Hereditary angioedema
ICE	Intercurrent event
ICH	International Council for Harmonisation
IDMC	Independent Data Monitoring Committee
IP	Investigational product
ISR	Injection Site Reaction
LLOQ	Lower limit of quantification
MedDRA	Medical Dictionary for Regulatory Activities
MSAP	Modeling and simulation analysis plan

Abbreviation	Term
PARM	Planned Analysis Review Meeting
PD	Pharmacodynamic
PK	Pharmacokinetic
PP	Per-protocol
PT	Preferred term
Q1	First quartile
Q3	Third quartile
Q1M	Once monthly
Q2M	Every 2 months
SAE	Serious adverse event
SAP	Statistical analysis plan
SC	Subcutaneous
SD	Standard deviation
SDTM	Study Data Tabulation Model
SMQ	Standardised MedDRA Query
SOC	System organ class
TEAE	Treatment-emergent adverse event
TLF	Tables, listings, figures
T _{max}	Time to reach maximum plasma concentration
WHO	World Health Organization

2 Purpose

This Statistical Analysis Plan (SAP) provides a detailed and complete description of the planned statistical analyses of the Study CSL312_3003 to support the Clinical Study Report (CSR).

This SAP complies with the International Council for Harmonisation (ICH) E9 'Statistical Principles for Clinical Trials' and E9(R1) 'Statistical Principles for Clinical Trials: Addendum on Estimands and Sensitivity Analysis in Clinical Trials', and is based upon the following study documents:

- Clinical Study Protocol Amendment 3, dated 9 January 2025
- electronic Case Report Form (eCRF), Version dated 30 Jan 2025

Population pharmacokinetic (PK) analyses are described within the modeling and simulation analysis plan (MSAP) and reported separately.

Mock tables, listings, and figures (TLF) shells are provided in a separate supporting document.

All decisions regarding the final analysis of the study results, as defined in this SAP, have been made before database lock (DBL) of the study data. Deviations from the planned analyses in this SAP will be detailed in the CSR.

3 Study Design

This is a multicenter, open-label, phase 3b pediatric study designed to investigate the safety, PK / pharmacodynamics (PD), and efficacy of subcutaneous (SC) administered CSL312 in the prophylactic treatment of hereditary angioedema (HAE) in children 2 to 11 years of age. The study schematic is shown in [Figure 1](#). The study will enroll a target sample size of approximately 20 subjects to ensure that at least 15 subjects complete 12 months of treatment.

[figure not shown]
The following subjects will be eligible to participate in this study if they meet all eligibility criteria:

- CSL312-naïve pediatric subjects with C1-esterase inhibitor (C1-INH) HAE type 1 or 2

CSL312 will be administered SC at a dose of 100 mg once monthly (Q1M; subjects 6 to 11 years of age) or every 2 months (Q2M; subjects 2 to 5 years of age) for at least 12 months.

The study will consist of a Screening Period, an open-label Treatment Period, and Follow-up Period. The Follow-up Visit takes place 3 months after last dose of CSL312. Subjects who complete the study have the option to continue treatment with CSL312 or another prophylactic treatment without a scheduled follow-up. Subjects who do not choose the post-study access program or another prophylactic treatment will complete the Follow-up Visit as mandated in this study.

Figure 1 Overall Study Schema

C1-INH = C1-esterase inhibitor; HAE = hereditary angioedema.

^a The Follow-up Visit may be conducted via telephone instead of at study site. Assessments / tests may be omitted if the Follow-up Visit is conducted via telephone. The Follow-up Period in this study is not applicable for subjects who choose to continue to receive CSL312 (and meet the criteria to participate in a post-study access program) or another prophylactic treatment. Subjects who do not choose the post-study access program or another prophylactic treatment will complete the Follow-up Visit as mandated in this study.

